9.2. Statistical Analysis of Safety Data

Descriptive statistics will be calculated on the safety parameters using the ITT population. The proportion of subjects with treatment-emergent adverse events will be tabulated and presented by treatment and Medical Dictionary for Regulatory Activities (MedDRA) System Organ Class. Vital signs, LSR scores and clinically relevant abnormal laboratory results will also be tabulated and presented by study medication. No inferential testing will be performed.

Data from all randomized subjects will be presented and summarized. Safety summaries by study medication group will include listings by study medication of adverse events incidences within each MedDRA System Organ Class, and changes from pre-application values in vital signs. Adverse event summaries will be presented by study medication showing the proportion of subjects experiencing adverse events, both overall and by MedDRA System Organ Class.

9.3. Interim Analysis

An interim Analysis will not be conducted for this study.

10. QUALITY CONTROL AND QUALITY ASSURANCE

10.1. Protocol Amendments

No changes from the final approved (signed) protocol will be initiated without the prior written approval or favorable opinion of a written amendment by the IEC/IRB, except when necessary to eliminate immediate safety concerns to the study subjects or when the change involves only logistics or administration. The principal investigator and the sponsor will sign the protocol amendment.

10.2. Protocol Deviations, Violations and Exceptions

A protocol deviation is non-adherence to protocol-specific study procedures or schedules that does not involve inclusion/exclusion criteria, primary objective variable criteria, and/or GCP

guidelines. Deviations are considered minor and do not impact the study. Deviations include study procedures that occurred outside the treatment windows (except for treatment application days).

A **protocol violation** is defined as any divergence from the protocol-specific inclusion/exclusion criteria, subject is administered a prohibited medication, primary objective variable criteria, and/or GCP guidelines. Protocol violations will be identified and recorded, by study center personnel, on the CRF.

As a matter of policy, sponsor/CRO will not grant **exceptions** to protocol-specific entry criteria to allow patients to enter a study. If under extraordinary circumstances such action is considered ethically, medically, and scientifically justified for a particular patient, prior approval from sponsor/CRO and the responsible IRB/IEC, in accordance with the Sponsor/CROs Standard Operating Procedure (SOP), is required before the patient will be allowed to enter the study. If investigative center personnel learn that a patient who did not meet protocol eligibility criteria was entered in a study (a protocol violation), they must immediately inform sponsor/CRO. Such subjects will be discontinued from the study, except in a rare instance following review and written approval by sponsor/CRO and the responsible IRB/IEC, according to the applicable SOP.

10.3. Data Management

Data will be collected using eCRFs that are specifically designed for this study. The data collected on the eCRFs will be captured in a clinical data management system (CDMS) that meets the technical requirements described in US 21 Code of Federal Regulations (CFR) Part 11. The CDMS will be fully validated to ensure that it meets the scientific, regulatory, and logistical requirements of the study before it is used to capture data from this study. Before using the CDMS, all users will receive training on the system and study specific training. After they are trained, users will be provided with individual system access rights.

The handling of data, including data quality assurance, will comply with regulatory guidelines, including ICH and GCP, and the sponsor/CRO SOPs and working instructions. Data management and control processes specific to this study will be described in a data management plan. At the end of the study, the database will be locked and the data will be released for reporting and statistical analysis

10.4. Quality Assurance

The study is conducted under the sponsorship of Aclaris Therapeutics, Inc. in compliance with the applicable regulatory requirements as well as applicable ICH guidelines, Helsinki Declaration, and in respect of the Aclaris Therapeutics, Inc. and/or sub-contractor SOPs for study conduct and monitoring.

Audits may be carried out by the Aclaris Therapeutics, Inc. or Aclaris Therapeutics, Inc.'s representatives and inspections may be performed by regulatory authorities or IRB/ECs before, during or after the study. The investigator will provide the auditing/inspecting group direct access to all study records (*e.g.*, CRFs, subject medical records, study medication dispensing records) and the investigational center study facilities. The investigator and study staff will be available and will assist the auditing/inspecting groups as appropriate.

11. TABLES AND LISTINGS: TITLES

Note: Mock tables and listings are provided in a separate document. They are intended to illustrate the format, layout and content of each table and listing. Final tables and listings may differ as appropriate. The mock tables and listings may include data from a previous study but will be superseded by data from the present study. Study identifier will be changed to A-101-WART-202. Treatment groups will be changed to A-101 Solution 45% and A-101 Solution Vehicle. Table numbers may be re-defined by the Medical Writer. Titles and Footnotes will be modified as required.

DEMOGRAPHIC DATA SUMMARY TABLES

Table 14.1.1	Disposition of Randomized Subjects – Study Completion/Subject
	Accountability
Table 14.1.2	Summary of Demographics – Randomized Population (Intent-to-Treat)
Table 14.1.3	Summary of Demographics – Safety Population
m 11 4444	

- Table 14.1.4
 Summary of Demographics Per Protocol Population
- Table 14.1.5
 Protocol Violations Randomized Subjects

EFFICACY DATA SUMMARY TABLES

Table 14.2.1	Target Wart Assessments: PWA Mean and Mean Change from Baseline, by Treatment and Visit – PP Population
Table 14.2.2	Target Wart Assessments: N and % PWA Responders with PWA Clear $(PWA = 0)$, by Treatment and Visit – PP Population
Table 14.2.3	Target Wart Assessments: N and % PWA Responders with PWA Clear or Near-Clear (PWA = 0 or 1), by Treatment and Visit – PP Population
Table 14.2.4	Treated Wart Assessments: N and % PWA Responders with All Treated Warts Clear (PWA = 0), Stratified by Number of Treated Warts, by Treatment and Visit – PP Population
Table 14.2.5	Treated Wart Assessments: N and % PWA Responders with All Treated Warts Clear or Near-Clear (PWA = 0 or 1), Stratified by Number of Treated Warts, by Treatment and Visit – PP Population
Table 14.2.6	Treated Wart Assessments: Mean of Per-Subject % of Treated Warts Clear $(PWA = 0)$, by Treatment and Visit – PP Population
Table 14.2.7	Treated Wart Assessments: Mean of Per-Subject % Change from Baseline PWA for Treated Warts, by Treatment and Visit – PP Population
Table 14.2.8	Durability of Response: N and % of Visit 10 Responders (PWA = 0) with $PWA = 0$ at Visit 13, by Active Treatment – PP Population
Table 14.2.9	Target Wart Assessments: PWA Frequency Distributions, by Treatment and Visit – PP Population
Table 14.2.10	Treated Wart Assessments: PWA Frequency Distributions, by Treatment and Visit – PP Population

Page 28 of 32 Date: 21 November 2017

SAFETY DATA SUMMARY TABLES

Displays of Study Medication Exposure and Adverse Events

- Table 14.3.1
 Study Medication Treatment Summary Safety Population
- Table 14.3.1.1
 Summary of Treatment-Emergent Adverse Events Safety Population
- Table 14.3.1.2
 Treatment-Emergent Adverse Events by System Organ Class Safety

 Population
- Table 14.3.1.3Treatment-Emergent Adverse Events in Decreasing Order of Frequency by
Preferred Term Safety Population
- Table 14.3.1.4Treatment-Emergent Adverse Events by Maximum Intensity, System OrganClass and Preferred Term Safety Population
- Table 14.3.1.5Treatment-Emergent Adverse Events Considered Treatment Related by
System Organ Class Safety Population
- Table 14.3.1.6Subjects Who Discontinued Study Drug Due to Adverse Events by System
Organ Class

Listings of Deaths, Other Serious and Significant Adverse Events

Table 14.3.2.1	Treatment-Emergent Serious Adverse Events by System Organ Class -
	Safety Population
Table 14.3.2.2	Treatment-Emergent Serious Adverse Events in Decreasing Order of
	Frequency by Preferred Term – Safety Population
Table 14.3.2.3	Treatment-Emergent Serious Adverse Events Considered Treatment Related
	by System Organ Class – Safety Population

Abnormal Laboratory Value Listing

Table 14.3.4.1	Lab Results	Outside Normal	Range,	Battery	Name:	Chemistry
----------------	-------------	----------------	--------	---------	-------	-----------

Table 14.3.4.2Lab Results Outside Normal Range, Battery Name: Hematology

Other Safety Data

- Table 14.3.5.1Treated Wart Local Skin Reactions (Evaluated by Subject), Frequency
Distribution by Symptom, Treatment and Visit
- Table 14.3.5.2Treated Wart Local Skin Reactions (Evaluated by Investigator), Frequency
Distribution by Symptom, Treatment and Visit
- Table 14.3.5.3Treated Wart Local Skin Reactions (Evaluated by Subject), Number and %
of Subjects for Each Symptom and Visit, With Target Wart Severity > 0
(None)

Table 14.3.5.4	Treated Wart Local Skin Reactions (Evaluated by Investigator), Number and % of Subjects for Each Symptom and Visit, With Target Wart Severity > 0 (None)
Table 14.3.5.5	Treated Wart Local Skin Reactions (Evaluated by Subject), Number and % of Subjects for Each Symptom and Visit, With Target Wart Severity > 1 (Mild)
Table 14.3.5.6	Treated Wart Local Skin Reactions (Evaluated by Investigator), Number and % of Subjects for Each Symptom and Visit, With Target Wart Severity > 1 (Mild)
Table 14.3.5.7	Mean and Mean Change from Pre-Treatment in Vital Signs: Systolic Blood Pressure (mm Hg)
Table 14.3.5.8	Mean and Mean Change from Pre-Treatment in Vital signs: Diastolic Blood Pressure (mm Hg)
Table 14.3.5.9	Mean and Mean Change from Pre-Treatment in Vital signs: Pulse Rate (beats/min)
Table 14.3.5.10	Mean and Mean Change from Pre-Treatment in Vital signs: Respiratory Rate (breaths/min)
Table 14.3.5.11	Mean and Mean Change from Pre-Treatment in Vital signs: Body Temperature (deg F)
Table 14.3.5.12	Concomitant Medications – Safety Population

SUBJECT DATA LISTINGS

16.2.1	Discontinued Subjects
Listing 16.2.1.1	Disposition of Subjects
16.2.2	Protocol Deviations
Listing 16.2.2.1	Protocol Deviations/Violations
16.2.4	Demographic Data
Listing 16.2.4.1	Demographic Information and Informed Consent
Listing 16.2.4.2	Medical History and Concomitant Conditions
Listing 16.2.4.3	Prior and Concomitant Medications
16.2.5	Compliance Data [See L6,7,7.1]
Listing 16.2.5.1	Study Medication Inventory
Listing 16.2.5.2	Randomization and Study Medication Application
16.2.6	Efficacy Data
Listing 16.2.6.1	Treated Wart Assessments: PWA Values by Treatment and Visit
Listing 16.2.6.2	Treated Wart Assessments: PWA responders with PWA Clear ($PLA = 0$)
	at Visit 10, by Treatment and Visit
Listing 16.2.6.4	Treated Wart Assessments: PWA Responders with PWA <= 1 at Visit 10, by Treatment and Visit
Listing 16.2.6.5	Treated Wart Dimensions – Length of Longest Axis, Values by
	Treatment
16.2.7	Adverse Event Listings
Listing 16.2.7.1	Mapping of MedDRA System Organ Class, MedDRA Preferred Term, and CRF Verbatim Terms
Listing 16.2.7.2	Treatment Emergent Adverse Events
Listing 16.2.7.2.1	Treatment Emergent Serious Adverse Events
Listing 16.2.7.3	Treatment Emergent Adverse Events Classified as Cutaneous by Investigator
16.2.8	Laboratory Listings
Listing 16.2.8.1	Female Pregnancy Tests
Listing 16.2.8.2	Lab Battery Name: Chemistry
Listing 16.2.8.3	Lab Battery Name: Chemistry: Results Outside Normal Range
Listing 16.2.8.4	Lab Battery Name: Hematology & Differentials
Listing 16.2.8.5	Lab Battery Name: Hematology & Differentials: Results Outside Normal Range

Page 31 of 32 Date: 21 November 2017

16.2.9	Other Listings
Listing 16.2.9.1	Treated Wart Local Skin Reactions (Evaluated by Subject), Values by
	Symptom, Treatment, and Visit
Listing 16.2.9.2	Treated Wart Local Skin Reactions (Evaluated by Investigator), Values
	by Symptom, Treatment and Visit
Listing 16.2.9.3	Vital Signs
Listing 16.2.9.3.1	Vital Signs: Observations Considered Abnormal and Clinically Relevant
Listing 16.2.9.4	Comments

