9.1. Local Skin Reactions (LSR)

The LSR assessment is the Investigator's assessment of the signs and the subject's assessment of the symptoms associated with irritation at the Target/Non-Target Wart site (*i.e.*, the Target/Non-Target Wart and the skin immediately surrounding the Target/Non-Target Wart exposed to study medication). The Investigator may refer to previous photographs to assist with these assessments only after the PWA has been performed.

The Local Skin Reaction signs to be assessed are:

- Erythema
- Edema
- Erosion
- Ulceration
- Vesicles/bullae
- Excoriations
- Scabbing.

The Local Skin Reaction symptoms to be assessed (by the Subject) are:

- Stinging/burning
- Pruritus (itch).

At Visits 2-13, the Investigator will evaluate the LSR signs at the Target/Non-Target Wart site(s) as follows:

- At visits where a study medication treatment or retreatment is performed:
 - \circ Perform an LSR assessment prior to any study medication application
 - $\circ~$ For treated Target and Non-Target Warts perform an LSR assessment 20 (±4) minutes after the Treatment Completion Time.

At Visits 2-13, the Subject will assess the LSR symptoms at the Target/Non-Target Wart site(s) as follows:

- At visits where a study medication treatment or retreatment is performed:
 - Perform an LSR assessment prior to any study medication application
 - For every treated Target and Non-Target Wart site, 10 (±4) minutes after the Treatment Completion Time, report the average of the severity of the LSR for all symptoms since completion of the study medication treatment.
 - At visits where no study medication treatment is performed:
 - Perform an LSR assessment.

The Investigator and subject should report the one integer that best describes the severity of each LSR sign or LSR symptom for the Target and Non-Target Wart sites using the scale below.

Page 36 of 53 Amendment 2 Version 3 Date: 05 December 2017
Local Skin Reactions			
Grade	Descriptor		
0	None		
1	Mild		
2	Moderate		
3	Severe		

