1. SYNOPSIS

	Protocol Number A-101-WART-202 Synopsis
Protocol Number:	Protocol Title: A Randomized, Double-Blind, Vehicle-Controlled, Parallel Group Study of A-101 Topical Solution Applied Once a Week in Subjects with Common Warts
Sponsor:	Phase of Development:
Aclaris	Phase 2

Study Drug Description:

A-101 Solution (45%) is a hydrogen peroxide solution that will be supplied in a glass ampule with an applicator to be applied to common warts (verruca vulgaris) on the trunk or extremities.

The study drug, A-101 (hydrogen peroxide) 45% Topical Solution (hereafter referred to as A-101) is a colorless solution that must be stored at room temperature (15-25° C or 59 -77° F). The blinded vehicle solution is packaged to match the active study drug and will be stored under the same conditions. **Study Objectives:**

Primary:

The main objective of this study is to evaluate the clinical effect of A-101 45% vs Vehicle when applied to 1 common Target Wart (verruca vulgaris) on the trunk or extremities.

Secondary:

The secondary objectives of this study include:

- Evaluate the clinical effect of A-101 45% when applied to all treated Warts (Target plus Non-Target Warts)
- Duration of response in all treated Warts (Target Warts plus Non-Target Warts)
- Safety of A-101 45%

Study Design:

This is a phase 2, randomized, multicenter study to evaluate the safety and efficacy of A-101 45% vs Vehicle in subjects with common warts on the trunk or extremities. Subjects may have up to a total of 4 treated common warts located on their trunk or extremities. Investigators will be required to identify 1 Target Wart for treatment with A-101 study medication. An additional 3 Non-Target Warts may be treated and followed throughout the study protocol therapy. All identified Common Warts will be treated once a week for 8 weeks. Subjects will be followed for 3 months after the last weekly treatment.

Approximately 120 evaluable subjects will be randomized to one of 2 treatment arms in a 1:1 ratio. The duration of study participation is anticipated to be up to a maximum of 155 days per subject. All subjects will be followed for at least 12 weeks after the last study medication treatment.

Safety will be evaluated based on clinical laboratory studies (hematology and clinical chemistry), vital signs, assessment of local skin reactions (LSRs), assessment of adverse events (AEs), and concomitant medication review.

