6.1. Local Skin Reactions (LSR)

The LSR assessment is the Investigator's assessment of the signs and the subject's assessment of the symptoms associated with irritation at the Target/Non-Target Wart site (*i.e.*, the Target/Non-Target Wart and the skin immediately surrounding the Target/Non-Target Wart exposed to study medication). The Investigator may refer to previous photographs to assist with these assessments only after the PWA has been performed.

The Local Skin Reaction signs to be assessed are:

- Erythema
- Edema
- Erosion
- Ulceration
- Vesicles/bullae
- Excoriations
- Scabbing.

The Local Skin Reaction symptoms to be assessed (by the Subject) are:

- Stinging/burning
- Pruritus (itch).

At Visits 2-13, the Investigator will evaluate the LSR signs at the Target/Non-Target Wart site(s) as follows:

- At visits where a study medication treatment or retreatment is performed:
 - Perform an LSR assessment prior to any study medication application
 - For treated Target and Non-Target Warts perform an LSR assessment 20 (±4) minutes after the Treatment Completion Time.

At Visits 2-13, the Subject will assess the LSR symptoms at the Target/Non-Target Wart site(s) as follows:

- At visits where a study medication treatment or retreatment is performed:
 - Perform an LSR assessment prior to any study medication application
 - For every treated Target and Non-Target Wart site, 10 (±4) minutes after the Treatment Completion Time, report the average of the severity of the LSR for all symptoms since completion of the study medication treatment.
- At visits where no study medication treatment is performed: • Perform an LSR assessment.

The Investigator and subject should report the one integer that best describes the severity of each LSR sign or LSR symptom for the Target and Non-Target Wart sites using the scale below.

	Local Skin Reactions	
Grade	Descriptor	
0	None	
1	Mild	
2	Moderate	
3	Severe	

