7.5. Treatment Compliance

Study medication use and accountability will be presented in a listing. Overall study medication use will be summarized by treatment group.

8. **PRESENTATIONS OF SAFETY INFORMATION**

Descriptive statistics by treatment group will be calculated on the safety parameters collected on or after Visit 3 using the Safety Population, defined as subjects who received at least one application of study medication. Safety summaries will include listings of clinical laboratory values and abnormal values, adverse events incidences within each Medical Dictionary for Regulatory Activities (MedDRA) System Organ Class, and changes from pre-dose values in vital signs. Adverse event summaries will be presented showing the proportion of patients experiencing adverse events, both overall and by MedDRA System Organ Class.

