8.5. Local Skin Reactions

Local Skin Reaction (LSR) scores will be summarized by frequency distributions for each symptom, by treatment group and visit. The proportion of subjects with with Severity > 0, and similarly for subjects with Severity > 1 will be presented for each symptom, by visit.

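### Read literally, the subject-level skin reaction tables leave out reactions confined to Non-Target Warts and all reactions after the first application, and no skin reaction summary separates pre- from post-application scores

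*SAP*

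**What the plan says.** **What is collected.** The SAP synopsis states: "Subjects may have up to a total of 4 treated common warts located on their trunk or extremities". At treatment visits, SAP 6.1 requires of both investigator and subject: "Perform an LSR assessment prior to any study medication application". A second score follows application. The subject's is due at 10 (±4) minutes, and Protocol 9.1 requires it "For every treated Target and Non-Target Wart site". The investigator's is due at 20 (±4) minutes, again for Target and Non-Target Warts.

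**What is summarised.** SAP 8.5 says that scores "will be summarized by frequency distributions for each symptom, by treatment group and visit". For the subject-level summary it says: "The proportion of subjects with with Severity > 0, and similarly for subjects with Severity > 1 will be presented". It names no wart set, no rule for combining several warts and no time point within a visit.

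**Table titles.** In SAP section 11, Tables 14.3.5.3 to 14.3.5.6 all begin with Treated Wart. The first two then give the number and percent "of Subjects for Each Symptom and Visit, With Target Wart Severity > 0"; the other two carry the same Target Wart condition with severity > 1. Tables 14.3.5.1 and 14.3.5.2 (frequency distributions) and Listings 16.2.9.1 and 16.2.9.2 refer to treated warts with no Target Wart condition.

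**Start of the safety window.** The opening paragraph of SAP section 8 restricts descriptive statistics to "safety parameters collected on or after Visit 3".

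**The concern.** Safety is a stated secondary objective, and the drug is a concentrated oxidising solution applied directly to skin, so reactions at the application site are a harm that the trial needs to describe well. A reader will want to know what share of subjects had a given reaction, and how severe it was. The four tables built to answer that do not count a subject with a severe reaction on a Non-Target Wart and none on the Target Wart.

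The Visit 3 start removes the first exposure. Visit 2 is also the one visit at which the plan has every identified wart treated; from Visit 3 to Visit 9, retreatment depends on the wart's status (Protocol 7.6).

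A score taken minutes after application and one taken before the next weekly application answer different questions: the immediate reaction, and what persists. Protocol 2.2 describes reactions in the previous study as generally transient. A by-visit figure with no time point cannot show whether that holds here.

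**Working it through.** The documents give no skin reaction rate, no distribution of wart counts and no within-subject correlation, so there is no planned figure to reproduce. The first and last steps rest on the text; the arithmetic is illustration on assumed inputs.

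**1. The literal rule**

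| Item | Collected | Counted in Tables 14.3.5.3 to 14.3.5.6 |
|---|---|---|
| Warts | Target and up to 3 Non-Target | Target only, by the title condition |
| Time points at a treatment visit | Before and after application | Not stated |
| Visits | 2 to 13 | 3 onward, by SAP section 8 |

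**2. Direction of the wart restriction.** Every subject with a Target Wart reaction also has a reaction on at least one treated wart. The Target Wart rate is therefore at most the any-wart rate. They are equal for subjects with one wart, or if all warts of a subject always react alike.

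**3. Possible size.** Let *p* be the per-wart rate, *k* the number of treated warts and ρ the intraclass correlation. Under a beta-binomial model, with a = p(1−ρ)/ρ and b = (1−p)(1−ρ)/ρ:

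P(any of k) = 1 − ∏ (b+i)/(a+b+i), for i = 0 to k−1.

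Take p = 0.10 (assumed) and k = 4:

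- ρ = 0.3: a = 0.233, b = 2.1. 1 − (0.900 × 0.930 × 0.946 × 0.956) = 24.3%.
- ρ = 0.5: a = 0.1, b = 0.9. 1 − (0.900 × 0.950 × 0.967 × 0.975) = 19.4%.
- ρ = 0.7: a = 0.043, b = 0.386. 1 − (0.900 × 0.970 × 0.982 × 0.988) = 15.3%.
- Limits: independence gives 1 − 0.9⁴ = 34.4%; perfect correlation gives 10%.

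The Target Wart table would show 10% in every case. A different model (equicorrelated latent normal) gives 25.9% at latent correlation 0.5 and 19.3% at 0.8. The two correlation scales are not interchangeable, but the direction is the same.

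**4. Mixed wart counts.** With 1, 2, 3 and 4 warts in 40%, 30%, 20% and 10% of subjects (assumed) and p = 0.10, the any-wart rate is 12.2% at ρ = 0.7 and 15.5% at ρ = 0.3. That is 1.2 to 1.6 times the Target Wart rate. Independence gives 18.6%, or 1.9 times. At p = 0.60 with the same mix, the rate is 66% to 73%, a ratio of 1.1 to 1.2. The ratio depends heavily on the assumed rate.

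**5. Pre- and post-application scores.** Take a pre rate of 10% and a post rate of 50% (assumed). Pooling records gives (10 + 50)/2 = 30%, below the post rate. Counting a reaction at either time gives 50% to 60%, at or above it. With pre 40% and post 20%, pooling gives 30%, above the post rate. The direction is not fixed, and the problem affects single-wart subjects too.

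**6. Visit 2.** The first post-application scores are taken at Visit 2, so a rule that starts at Visit 3 excludes all of them. Reactions still present a week later can appear in the Visit 3 pre-application score; those that resolved in between do not.

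**The case against.** Several points against the concern are fair.

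- **The Target Wart condition may not be settled.** The same titles begin with Treated Wart, and the methods text in SAP 8.5 has no such limit. SAP section 11 places the shells in a separate document, not available here, and allows titles to change. This stands: the plan contradicts itself, and the shells may resolve it. But the condition appears in all four titles, and the efficacy titles in the same section distinguish Target Wart from Treated Wart tables.
- **A Target Wart rate, labelled as such, is not biased.** It is a different quantity. One pre-identified wart per subject also compares the arms like for like, whereas a worst-wart rate depends on how many warts each subject has, and Protocol 7.2 describes no stratification on that. This stands as a reason to keep the Target Wart tables, not to make them the only subject-level summary.
- **Non-Target scores are not lost.** They fall within Tables 14.3.5.1 and 14.3.5.2 and the listings. This stands, but no title there promises a subject-level rate.
- **The Visit 3 limit conflicts with other text.** SAP 8.5 summarises by visit without it, and SAP 9.2 presents data from all randomized subjects. That makes it a conflict to reconcile; it does not prove that Visit 2 will be dropped.
- **These are descriptive tables with no inferential testing.** True; no efficacy conclusion depends on them.

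A reader might also infer more than the documents support: that the missing pre/post split lowers the rates (step 5 shows no fixed direction), that the shortfall falls mostly on the active arm (no arm-specific rates are given, and the relative gap can be larger where rates are low), or that the frequency tables count warts rather than subjects (neither SAP 8.5 nor the titles state the unit).

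**Conclusion.** The concern holds in a limited form. Followed as written, the plan's subject-level reaction rates omit subjects whose only reaction was on a Non-Target Wart, and omit reactions after the first application. Relative to an any-treated-wart rate, the Target Wart restriction can only lower the figure or leave it unchanged.

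The documents do not give the size. On an assumed 10% per-wart rate with four warts, 10% would be shown against about 15% to 24% at intraclass correlation 0.7 to 0.3; with one wart or perfect correlation the gap is zero. No general understatement factor should be quoted: every input is assumed, and the 1.9 in step 4 is the independence case.

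The missing pre/post split is a separate defect. It leaves the by-visit figures undefined, with no known direction of error.

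This is worth correcting before the tables are produced. It goes beyond missing detail, because two stated rules, the Target Wart condition and the Visit 3 start, give an incomplete account of local reactions.

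**What to change.** - **SAP 8.5 and Tables 14.3.5.3 to 14.3.5.6:** for each subject, visit and sign or symptom, take the worst grade over all treated warts and report the percent of subjects above 0 and above 1. Keep Target-Wart-only results as supplementary tables, labelled as such.
- **Wart set over time:** state whether warts that have cleared and are no longer treated still count at later visits.
- **Time point:** present pre- and post-application scores separately in Tables 14.3.5.1 to 14.3.5.6.
- **SAP section 8:** amend the Visit 3 start so that the Visit 2 post-application skin reaction scores are included, consistent with SAP 8.5.

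The cost is a little programming; the scores are already collected on every treated wart. The reported reaction rates may be less favourable than under Target Wart counting.
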